#### ***Secondary Outcomes (Aim 2) – Pain Characteristics for the Three Intervention Arms at 12 months***

Taper success (MEDD and pain intensity), pain interference, pain self-efficacy, and depression and satisfaction with social roles and activities will be assessed (for more details, see Appendix A). Specifically, depression and satisfaction with social roles and activities will be assessed using National Institutes of Health PROMIS short-form measures which are commonly used in pain research. These domains were identified by the Initiative on Methods, Measurement, and Pain Assessment in Clinical Trials as core outcomes. Web-based PROMIS assessment center software will calculate short-form T scores using Item Response Theory scoring algorithms that apply the Bayesian expected a posteriori method.

EMPOWER Patient-Centered Opioid Taper (received by all three study arms). Following study enrollment, all participants will engage with their EMPOWER clinician in a patient-centered prescription opioid tapering program. All opioid prescribing will be managed by the EMPOWER clinician. Opioid dose data will be sourced from study surveys and the patient's electronic medical record. All aspects of tapering will be individualized, including the timing of taper initiation, the dose reduction goal (set collaboratively with the patient), and the pace of the taper. The basic patient-centered opioid taper protocol will mirror the pilot methods described in Darnall et al. Importantly, complete opioid cessation will only be a goal if the patient chooses it. The recommended taper speed will be a 5% reduction of the starting dose, with one dose decrease per month until the patient is stable, without physical discomfort or psychological distress. Patients will be assessed at each visit; dose decreases or increases in taper speed will only occur after consultation with and consent from the patient. Patients will have the choice to set the pace of their taper, pause their taper, or withdraw from the taper or the study at any time. The taper will not be unidirectional: EMPOWER will not restrict needed opioid increases for acute pain or for patients with poor responses to the taper. Participation in the study will not prevent patients from receiving any needed medical care. Patients will not be removed from the study if they increase their opioid dose; on the contrary, we will seek to follow these patients to understand their experiences, responses, and unmet treatment needs.

Clinicians may use the electronic CHOIR opioid taper tool to create a taper schedule that remains flexible based on patient responses to prior dose reductions. Micro-dose reductions will be recommended for the first few decrements, followed by dose reductions as tolerated, not exceeding a 10% opioid dose reduction per month. Recommendations will include tapering one opioid at a time and avoiding

concurrent tapering of other medications. Participants will receive in-person or online medical follow-ups with their EMPOWER clinician approximately every three to four weeks. Participants will complete weekly and monthly CHOIR symptom surveys, which will be reviewed during medical follow-ups to determine whether reported withdrawal symptoms are related to the taper or are unrelated (e.g., seasonal allergies). If CHOIR detects severe or worsening symptoms indicative of participant struggle or deterioration, immediate (real-time) electronic alerts will be sent to the participant, clinic, and prescribing clinician, with follow-up actions based on symptom severity.

The study protocol will encourage the use of adjuvants within the scope of normal clinical practice and training and will not restrict other analgesic prescribing, such as initiating SNRI medications. The protocol will provide guidance on reducing short- and long-acting opioids and recommend tapering one medication at a time. Concurrent tapering of other medications will be discouraged.

The EMPOWER taper program may only be administered by a prescriber clinician trained in EMPOWER methods.

*CHOIR Opioid Taper Tool.* EMPOWER will include an electronic taper calculator allowing clinicians to input the patient's current dose, number of daily doses, desired taper timeframe, taper goal, and taper pace. The tool will generate precise guidance for doses/pills per dose daily over several months. Because the taper will be flexible, the opioid taper tool can be used multiple times to recalculate a patient's taper plan based on new circumstances, such as a desired taper pause or a patient's request to adjust the taper speed.

#### *Study Arms*

**(1) EMPOWER Taper + Cognitive Behavioral Therapy for Chronic Pain (pain-CBT).** Pain-CBT is a behavioral treatment that reduces chronic pain and its impacts through patient education, skills acquisition, and social support. Research on pain-CBT indicates benefits for reducing pain intensity, pain catastrophizing, depression, and the social impact of pain. CBT is considered the gold-standard psychobehavioral treatment for pain, with other behavioral treatments demonstrating non-inferiority but not superiority. A general pain-CBT therapist manual and corresponding patient workbook were developed for the EMPOWER study (EMPOWER CBT). A relaxation MP3 audio file accompanies the patient workbook. Consistent with general pain-CBT, the EMPOWER CBT protocol includes interactive discussion, pain education, relaxation training practice, goal setting, cognitive restructuring, problem-solving, and action planning, with home exercises incorporated into each session. Participants will learn to effectively manage their pain and symptoms while working towards achieving the goals that matter to them. A mental health will deliver the eight-week group intervention to cohorts of patients (N=8–18) assigned to this arm. Intervention sessions will be delivered weekly and last two hours. To ensure consistency across all study sites and cohorts, therapists will be trained in the common eight-session CBT protocol, with competency assured by Director [name]. The structured format of the CBT intervention ensures treatment fidelity, with the trained therapists using PowerPoint slides (for didactic content), corresponding worksheets from the participant workbook, and optional reading from an additional book. The study coordinator will be present at each treatment session and facilitate intervention fidelity by ensuring participants have corresponding materials, including the relaxation audio. Participants assigned to this intervention arm will not receive CPSMP during the study period. No other aspects of pain care will be constrained.

**(2) EMPOWER Taper + The Chronic Pain Self-Management Program (CPSMP).** CPSMP is an evidence-based behavioral treatment delivered by two certified healthcare clinicians or peer co-leaders with lived experience in successful pain self-management. Certification as a CPSMP leader requires 24 hours of training over four days. The CPSMP manualized protocol includes patient education about pain and strategies for effective self-management of pain, its impacts, and other symptoms. Based on self-efficacy theory, CPSMP is delivered in six weekly 2.5-hour group sessions to cohorts of 8–18 participants. All participants receive a book on pain self-management and an exercise CD. Like pain-CBT, CPSMP incorporates interactive discussions, relaxation training, action planning, and home exercises into each session. Patients learn to live better with chronic pain by making daily choices that support improved health and function. Participants assigned to this arm will not receive group pain-CBT during the study period. No other aspects of pain care will be constrained, including individual psychological treatment; receipt of non-study treatments will be tracked.

Prior research has shown that pain-CBT and CPSMP have both shared and distinct effects, suggesting some individuals may respond better to one treatment than the other. However, no evidence currently exists to guide a best-practice choice between the two. While pain-CBT and CPSMP are both effective for chronic pain, they have not been tested within an active opioid reduction protocol. We hypothesize that these behavioral interventions will help patients reduce opioids and associated risks, manage pain, and restore function in ways superior to opioid reduction alone.

**(3) EMPOWER Taper Only (usual care).** Participants assigned to this intervention arm will participate in the voluntary EMPOWER patient-centered opioid tapering program and will not receive group pain-CBT or CPSMP during the 12-month study period. No other aspects of pain care will be constrained.

#### **Virtual Format for Behavioral Treatment Groups**

**Background:** In March 2020, the COVID-19 pandemic led to social distancing safety requirements, which prevented the continuation of in-person delivery of our behavioral treatment groups. In response, with PCORI approval, we demonstrated the feasibility of virtual groups by piloting a virtual option with participants who were already enrolled in the study (i.e. enrolled prior to 03/26/2020). We now offer virtual (live, online) delivery of our behavioral treatment groups as another option for all participants including new enrollments. Due to ongoing and unpredictable COVID-19 restrictions on group gatherings, live virtual treatment delivery is essential to ensure successful completion of our RCT.

Content: Virtual pain-CBT and CPSMP treatments are delivered exactly as outlined in the protocol where the same content and materials (e.g., participant workbooks, presentation slides, etc.) by live facilitators with live participants. The only difference between virtual and in-person is the video format in the virtual groups and materials are distributed via traditional mail instead.

Platform – Each site delivers the virtual treatments using a HIPAA compliant and secured platform endorsed by their respective institution (Zoom at Stanford and Colorado, VA Video Connect at the Phoenix VA, and WebEx at Intermountain Health). The platforms are broadly utilized for telehealth at the sites.

Facilitator Training – To assure high-quality and standardized delivery, the facilitators who conduct the in-person groups at each site, are also the same facilitators delivering the virtual treatments. Additionally, we centralized our virtual system across Stanford Pain, Stanford Primary Care and Colorado where we have Stanford psychologists (or Telligen peer leaders) leading a cohort comprised of both Stanford and Colorado participants. As closed payer systems, Phoenix VA and Intermountain Health do not permit external services. The facilitators practiced delivering the programs on the virtual platform up to three times before the start of the first series.

Participant Training – The facilitators, study coordinators, and the core manager collaborated in developing materials to prepare participants to successfully engage in the virtual groups. Before the first session, the local study coordinator conducts an orientation with each participant to review how to use the platform and etiquette expectations (e.g., be situated in a private, quiet place during each session). Please see accompanying documents (Study Coordinator Procedures/Script, Group Telehealth Agreement, Facilitator Work Flow and Guidelines, Welcome to the Group, Welcome Letter, and Zoom Application Instructions).

#### Patient-Centered Opioid Tapering (taper-only, no behavioral treatment)

Virtual Format - Each recruitment site enhanced their clinic schedules to make virtual medical visits more accessible to patients at the onset of the COVID-19 pandemic in March 2020. Participants continue to have the option to schedule an in-person or virtual appointment for their follow-up visits with their EMPOWER clinician. All sites had an established telehealth system, which allowed a smooth transition into conducting more virtual visits. Video and messaging features are included in the telehealth system. For participants who do not have access to a smartphone or computer, the Phoenix VA loans tablets to patients to address this issue.

*Institutional Review Board (IRB).* The study will adhere to the common protocol and procedures approved by local IRBs at all study sites.

#### **Sample Size Calculations and Study Power**

The power calculation is primarily based on the study aims for comparative effectiveness. The original power calculation was for  $N = 850$ , with  $N = 750$  patients completing the month-12 survey. The study sample size was later reduced to  $N = 489$  participants completing the month-12 survey ( $n = 163$  patients per intervention arm on average). As a result, the study's power is lower than initially planned but remains adequate for the objectives, summarized as follows:

*Hypothesis 1a.*  $N = 163$  Taper Only participants provide 80% power to confirm that the taper success rate is above 40% at a two-sided significance level of 0.05, when the true success rate is 51.5%.

*Hypothesis 1b.* Comparing the taper success rate between  $n = 140$  Taper Only participants with an initial dose  $< 200$  MEDD and  $n = 23$  Taper Only participants with an initial dose  $\geq 200$  MEDD, the expected 95% confidence interval (CI) for the difference in success rates is [-22%, 22%], assuming a true taper success rate of 50% independent of the initial dose. The width of the CI increases by only 24% due to the sample size reduction.

*Hypothesis 2a.*  $N = 163$  participants per intervention arm provide 80% power for detecting a taper success rate difference of 40% versus 53.5% at a two-sided significance level of 0.05.

*Hypothesis 2b.*  $N = 163$  participants per intervention arm yield an expected 95% CI of [-11%, 11%] for estimating the difference in taper success rates between the Taper + pain-CBT and Taper + CPSMP arms, assuming a taper success rate of 50% in both arms.

*Hypothesis 2c and 2d.*  $N = 163$  participants per intervention arm provide 80% power to detect a between-group difference of 0.311 standard deviation in the 12-month change of continuous outcomes using a two-sample t-test at a two-sided significance level of 0.05.

We also assume an annual drop off rate is less than 19% and we will include all drop outs in our ITT analyses. We will enroll a total of 594 patients to assure the minimum group size requirements for analysis of comparative effectiveness.

#### **Statistical Analysis Plan**

*Aim 1:* Reduce or contain prescription opioid use while maintaining pain control.

*Hypothesis 1a:* We will estimate the proportion of patients achieving patient-centered opioid taper success and test whether this proportion exceeds 40% (treatment success estimate derived from Darnall et al.). We will estimate the binomial proportion of patients with opioid taper success and use the exact test to test whether the proportion is greater than 40%.

*Hypothesis 1b:* We will compare opioid tapering success rates among patients in different initial opioid dose categories: Low (10–49 MEDD), Moderate (50–89 MEDD), High (90–199 MEDD) and Super-High ( $\geq 200$  MEDD).

**Aim 2:** Examine the balance in key patient characteristics such as initial opioid dose, pain intensity, and functional measures separately for the three interventions arms. We will use Chi-square or Fisher's exact tests to compare success rates between opioid dose groups.

***Hypothesis 2a:*** We will compare the intervention success rate of 500 patients in behavioral intervention arms (pain-CBT and CPSMP) with 250 patients receiving patient-centered opioid tapering only (no behavioral intervention; Taper Only). We will use a Chi-square test to compare the success rate between groups. We will apply logistic regression to adjust for baseline covariates.

***Hypothesis 2b:*** We will estimate the difference in intervention success rates between pain-CBT and CPSMP arms using an intention-to-treat procedure and construct 95% CIs for the difference.

***Hypothesis 2c:*** We will compare changes in pain intensity, pain interference, and depression scores (baseline to 12 months) between the pain-CBT and Taper Only as well as between the pain-CBT and CPSMP arms using two-sample t-tests. We will apply an analysis of covariance based on multiple regression to adjust for baseline covariates.

***Hypothesis 2d.*** We will compare improvements in satisfaction with social roles and activities, and self-efficacy for Taper + CPSMP against Taper + pain-CBT and Taper Only.

We will compare the intervention success rate between participants who received the behavioral interventions with participants who received Taper Only using Fisher's exact test. The difference in success rates between Taper + pain-CBT and Taper + CPSMP will be assessed with 95% confidence intervals (CI) to determine equivalence. Secondary outcomes—including pain intensity, pain interference, depression, self-efficacy, and satisfaction with roles and activities—will be compared between Taper + pain-CBT and Taper Only and between Taper + pain-CBT and Taper + CPSMP at months 6 and 12 using mixed effects model for repeated measurements regression. This analysis will incorporate baseline, month 6, and month 12 outcomes as dependent variables, with an unstructured variance-covariance matrix for within-subject correlations.

***Exploratory Hypothesis 2e:*** We will separately estimate the probability of opioid escalation by intervention arm (pain-CBT, CPSMP and Taper Only).

For exploratory hypotheses, the probabilities of opioid escalation by intervention group will be estimated and compared with Fisher's exact test. Post-hoc analyses will use logistic regression to examine associations between baseline characteristics and tapering success. There is no correction for multiple comparisons. Heterogeneity of treatment effects will be explored by splitting the population into training and validation sets of equal sizes. Logistic regression with lasso regularization will identify baseline features predicting tapering success in each intervention group. These models will be applied to testing sets to identify the subgroup with the highest predicted success under Taper + pain-CBT, and success rates will be compared across intervention arms within the subgroup. Intervention effects will be also estimated in predefined subgroups.

Heterogeneity of treatment effects will be explored for each intervention arm considering gender, age, race, initial opioid dose, baseline depression, and anxiety level.

***Access and Intervention Participation.*** The comparison across interventions will be performed according to the intention-to-treat principle. Additional comparisons based on the actual intervention received will be conducted as a sensitivity analysis. We will also study the effect of intervention participation and on treatment outcomes. To this end, we will perform regression analyses to examine the association between the success rate for opioid weaning and other outcomes with session attendance for the pain-CBT and CPSMP arms, separately, while adjusting for identified confounding factors affecting compliance. We will also investigate how baseline factors, such as socioeconomic status, affect the level of compliance.

***Virtual Behavioral Treatment Groups: Comparison of participants who receive in person vs. virtual treatment -*** We will examine mode of delivery as a potential covariate in our analytic models, and study statistician [name] will both advise and implement. Outside of this issue of treatment delivery mode, we must also recognize that COVID itself has introduced a new variable in the study. We will be examining COVID impacts, as well. In regards to the group size and effectiveness of the intervention, the size of the virtual groups are comparable to the size of the in person groups where most groups have an average size of 4 participants. Facilitators stated larger groups (more than 4 participants per cohort) usually provide a more dynamic experience with diverse interactions. While in smaller groups, participants have a chance to go into more detail regarding the skills they are learning and using and any barriers that arise.

***Sensitivity Analysis.*** We will perform sensitivity analyses to account for missing data and non-completion of behavioral interventions. In addition, we will consider an alternative definition of taper success, replacing the 50% reduction in opioid dose with a 30% reduction in opioid dose. A 30% change has been cited as a benchmark for a moderately clinically important difference in the chronic pain literature. Similar analyses will be conducted with this new endpoint as part of the sensitivity analyses.

Statistical analysis will be completed using SAS Enterprise Guide Version 8.3 and R Version 4.1.1.

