## Study Goals and Objectives

### *Aim 1: Reduce or Contain Prescription Opioid Use While Maintaining Pain Control.*

Hypothesis 1a. At one year, 40% of participants in the Taper Only group (no behavioral treatment) will successfully reduce prescription opioids by  $\geq 50\%$  in MEDD without worsening pain intensity, pain interference, or satisfaction with social roles and activities at 12 months.

Hypothesis 1b. Success with patient-centered opioid tapering will not be associated with the starting MEDD.

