### ***Study Outcomes***

#### ***Primary Outcome (Aim 1) – Taper Success at 12 months***

Taper success will be defined as a  $\geq 50\%$  reduction in MEDD from baseline to 12 months without significant pain intensity increase ( $\leq 1$ -point increase) or no opioid increase with significant pain relief ( $\geq 2$ -point decrease in pain intensity). Please see Appendix A, Data Measurement Plan, for more details.

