Satisfaction with Group Intervention	Pain-CBT and CPSMP participants will rate their level of satisfaction with their assigned intervention, and separately, with their group instructor on a 7-point rating scale (0 = “not at all satisfied” to 6 = “extremely satisfied”).		x***	x***	
Life Changes survey	Items assess changes to employment, disability status, and/or major life events (new child, loss of a loved one, divorce, major illness, etc.).				x
Study Satisfaction	Patients will rate their level of satisfaction with the study (0 = “not at all satisfied” to 6 = “extremely satisfied”). They may input free text responses and we will monitor these closely.				x
Study Effects	Assesses patient-reported effects (positive and negative) as a result of participating in the study.				x
Patient's Global Impression of Change (PGIC) 	Single item assessing patient's impression of general improvement as a result of participating in the study.				x
COVID-19	Assesses impact of COVID-19 on participants.	x		x	x
Pain Interference	A nine-item Brief Pain Inventory questionnaire measures the level of pain-related interference during the past twenty-four hours across seven domains (such as mood, general activity, etc.) on a scale of 0 (does not interfere) to 10 (completely interferes). Higher scores signify worse pain interference. A total pain interference score will be created by averaging the seven domain scores for each participant. 	x		x	x
Opioid Dose	Participants will self-report their daily prescribed opioid type(s) and dose(s). Daily opioid doses will be converted to a total standardized morphine equivalent daily dose (MEDD) using the 2016 CDC Guidelines for conversion factors including using the escalation of the factor for methadone (i.e. methadone's conversion factor increases at higher doses). 				

\* Monthly questionnaires will be distributed at months 1-5 and 7-11. They will not be distributed at months 6 and 12.

\*\* Group Treatment Attendance Form will only be completed while participant is currently in pain-CBT or CPSMP interventions.

\*\*\* Satisfaction with Group Intervention Form will be distributed following the first and final session of the intervention course only.

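### Hypothesis 1b groups patients by the same baseline MEDD that is the reference for taper success, so baseline dose error that does not recur at month 12 tilts success upward with starting dose.

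*Combined protocol and SAP*

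**What the plan says.** Study Goals and Objectives states Hypothesis 1b as: "Success with patient-centered opioid tapering will not be associated with the starting MEDD". For its analysis the SAP says: "We will compare opioid tapering success rates among patients in different initial opioid dose categories", with cut-points at 50, 90 and 200 MEDD. The test appears a few lines later, in the Aim 2 paragraph: Chi-square or Fisher's "exact tests to compare success rates between opioid dose groups".

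Study Outcomes defines taper success by two routes. The first is at least a 50% "reduction in MEDD from baseline to 12 months without significant pain intensity increase". The second requires that the dose has not risen and that pain has fallen by at least 2 points. Both routes use the baseline dose as reference. The 30% endpoint under Sensitivity Analysis keeps the same reference.

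On where the dose comes from, the taper description says "Opioid dose data will be sourced from study surveys and the" electronic medical record. The Opioid Dose row of Appendix A mentions patient self-report only. No rule says which source prevails, or whether one source serves for grouping and the other for the outcome.

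**The concern.** When one measured value both assigns the dose category and serves as denominator of the outcome, an error in it acts twice. A value that is too high moves the patient towards a higher category and makes the month-12 dose look like a larger cut. A value that is too low does the reverse. The result is a positive relation between starting dose and success that need not exist.

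The direction matters because 1b predicts no association. If high-dose patients truly do worse, the artefact pulls the observed difference towards zero, and the analysis can appear to support the hypothesis. The bias does not shrink as patients are added, and the planned tests do not allow for it.

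**Working it through.** **1. The plan's own figure.** Sample Size Calculations compares n = 140 below 200 MEDD with n = 23 at or above it, "assuming a true taper success rate of 50% independent of the initial dose".
- SE = √(0.25/140 + 0.25/23) = 0.1125.
- Half-width = 1.96 × 0.1125 = 0.2205, so the stated ±22 points reproduces.
- Stated widening of 24%: √(250/163) − 1 = 23.8%, which also reproduces.

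**2. Why the coupling biases, and when it does not.** On the log scale let b be true baseline dose, r the true log ratio of month-12 to baseline dose (independent of b), e the baseline error and u the month-12 error. Let both errors have SD σ and correlation ρ, and be independent of b and r. The category uses b + e. The outcome uses r + u − e.
- Covariance = Cov(e, u) − Var(e) = −(1 − ρ)σ².
- A negative value means that a higher recorded start goes with a larger apparent cut.
- At ρ = 0.5 the covariance is halved. At ρ = 1 it is zero. A uniform over-report has no variance, so it gives no gradient.
- If the category instead uses a record value b + w, with w independent of e and u, the covariance is zero. If w correlates 0.5 with e (same SD, independent of u), half remains.

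**3. Size by simulation.** The documents give no error rate, dose spread or taper variability, so all of these are assumed. Log baseline dose is normal, cut off below 10 MEDD, with 23/163 at or above 200. The log dose ratio is centred on log 0.5, so true success on the dose criterion is 50% in every category. Error log-SDs of 0.1, 0.2 and 0.3 correspond to one-SD factors of e^0.1 = 1.11, e^0.2 = 1.22 and e^0.3 = 1.35. Entries are the difference, ≥200 minus <200 MEDD, in percentage points.

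| Setting | 0.1 | 0.2 | 0.3 |
|---|---|---|---|
| No true association, both success routes, assumed pain outcomes | +0.9 | +3.0 | +6.2 |
| No true association, dose criterion only, range over baseline log-SD 0.8–1.0 and ratio log-SD 0.5–0.8 | +0.8 to +1.8 | +3.2 to +6.2 | +6.7 to +11.5 |
| True 10-point deficit, both routes | −8.6 | −5.0 | −0.6 |
| True 10-point deficit, dose criterion only (log-SDs 1.0 and 0.8) | −8.2 | −4.7 | −0.1 |
| Same, grouped by an independent record dose | −9.1 | −8.0 | −6.7 |

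With no true association, grouping by an independent record gives 0.0 ± 0.1 points throughout. At error log-SD 0.3 (dose criterion only, log-SDs 1.0 and 0.8), correlation 0.7 between the two times leaves +2.3, fully persistent error gives −0.1 and month-12-only error gives +0.1. A uniform 20% baseline over-report gives 0.0. If 5% or 10% of baseline reports are wrong by a factor of 2, the false gap is +1.9 or +3.6.

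**4. Against the stated precision.** Two-sided power for a difference d is Φ(d/SE − 1.96) + Φ(−d/SE − 1.96).
- True 10 points: 0.100/0.1125 = 0.889, power about 14%.
- Seen as 4.7 (error 0.2, planned grouping): 0.418, about 7%.
- Seen as 8.0 (error 0.2, record grouping): 0.711, about 11%.

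**The case against.** Four arguments against the point have weight.

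- **Not every error does this.** A reader might infer that any mistake in the baseline dose creates a gradient. Step 2 shows otherwise. The same patient answers the same question each time, so a wrong strength or a drug listed twice could recur at month 12 and partly or wholly cancel.
- **A single self-report is not established.** Appendix A read alone suggests one, but the taper description names the medical record as a second source. What can be shown is that the two places are not reconciled. How much error would survive if both sources are used is unknown.
- **Imprecision is the larger limit.** With 23 patients in the top group, a real 10-point deficit would usually be missed with or without the coupling. A reader might attribute a finding of no association to the coupling; at the stated sample size the wide interval is the likelier cause.
- **The remedy is not clean.** The survey asks for the prescribed dose, which the record also holds, so errors may be shared. A real temporary dose rise before baseline is arguably the starting dose rather than an error, and it would appear in the record too.

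These arguments limit the size and generality of the point. They do not remove it: no safeguard is written, the direction favours the hypothesis, and the stated ±22 points covers sampling error only.

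**Conclusion.** The point holds with limits. Hypothesis 1b relates success to the value against which success is measured. Baseline error that differs between patients and is not fully repeated at month 12 biases the dose contrast upward. Under assumed error log-SD 0.1 to 0.3 with the two-route definition, the false gap is about +1 to +6 points, and a true 10-point deficit appears as −8.6 to −0.6. Error correlated 0.5 over time roughly halves the bias, uniform or fully persistent error removes it, and near-exact reports leave less than 1 point.

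These sizes rest on assumed error, dose spread and pain outcomes. The documents do not support saying that the bias is large in this trial, or that it would decide 1b. They do support saying that it is unaddressed, and that a non-significant 1b result should not be read as evidence of no association on this analysis alone. The logistic and lasso models share the problem wherever initial dose is a predictor of success.

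**What to change.** In the SAP text for Hypothesis 1b:

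1. State which source, survey or medical record, supplies the baseline dose used as denominator, and reconcile the taper description with Appendix A.
2. Add a pre-specified 1b analysis that groups patients by the last prescribed MEDD in the medical record before the baseline survey, with the survey value kept as denominator.
3. Report this beside the planned analysis, each with its confidence interval. Do not conclude that there is no association if the two diverge, and say beforehand what will count as divergence.

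The cost is SAP wording and one extra analysis. The record is already consulted for eligibility and named as a dose source, so no new visits are needed. There are three downsides. Some patients, such as those recruited through community advertising, may lack a usable record; they should be left out of the added analysis, because giving them the survey value would restore the coupling. Grouping by the record slightly dilutes a true gradient through misclassification. If record and survey errors are correlated, the bias is only partly removed: about half remains at a correlation of 0.5. For these reasons the record-based grouping is better added than substituted for the planned category.
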